#### **Assessment of Treatment Outcome and Time Course.**

Primary Measures: (1) Binge-eating frequency (EDE); (2) weight (measured weight and height and BMI); for Stage 2 LDX vs Placebo test: "Relapse" to DSM-5 threshold of once-weekly binge eating on EDE

Secondary Measures: (1) "remission" (zero binges past 28 days on EDE; eating disorder pathology (EDE global), depression (BDI-II); for exploration of mediators: (2) eating behaviors (EDE, TFEQ, FCI-II), executive control and impulsivity (BIS-11, DDT, Trails) and selected metabolic measures (lipid profiles, HbA1c, blood pressure, HR) to characterize metabolic outcomes and allow comparison with RCTs for LDX and NB.

**Figure 2.** Grid depicting when each measurement is obtained

Assessment Points	BASELINE (2 MTG)	DURING RX STAGE 1 1-MONTH	DURING RX STAGE 1 2-MONTH	POST RX STAGE 1 3-MONTH	DURING RX STAGE 2 4-MONTH	DURING RX STAGE 2 5-MONTH	POST RX STAGE 2 6-MONTH	6 AND 12- MO FOLLOW- UP (18 MONTH TOTAL)
MINI Psychiatric Interview, Height, Credibility,	•							
EDE Interview, SF-12, GPAQ, Lipid Profile, HbA1C, Glucose	•			•			•	•
EDE-Q-I, BDI-II, GLTEQ, Weight, BP, HR	•	•	•	•	•	•	•	•
TFEQ-Restraint	•	•		•			•	•
DDT	•	•		•			•	
FCI-II, PFS	•	•		•	•		•	
BIS-11	•	•		•	•		•	•
ELOCS	•	•		•				
Trails, YFAS, BRS, Amphetamine Testing	•			•			•	
Placebo Ratings					•		•	
Start of New Treatments				•			•	•
Medical History Creatinine w/ EGFR PSQI	•			•				
Adverse Events		•	•	•	•	•	•	
Insulin	•			•				

Liver Function	•			•	• (Non- responde rs only)			
Pregnancy Test	•			•				

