**Inclusion Criteria:**

1. Be in the age range  $\geq 18$  years of age and  $< 65$  years of age.
2. Have a BMI  $\geq 30$  and  $\leq 50$  (or BMI  $\geq 27$  with a metabolic disorder associated with obesity).
3. Meet diagnostic criteria for binge eating disorder (per DSM-5).
4. Be an otherwise healthy subject (except for obesity-related metabolic problems that are not deemed uncontrolled), as determined by physical examination and EKG, medical history and treatment, and lab testing which will be reviewed by the study physician.
5. Read, comprehend, and write English at a sufficient level to complete study-related materials.
6. Provide a signed and dated written informed consent prior to study participation.
7. Be available for participation in the study for up to 18 months (3 month + 3 month treatment plus 12 month follow up).

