#### **Medication Titration & Taper.**

**LDX:** Participants will have up to three weeks of up-titration: one pill daily (30 mg/day; 1 week), then one pill daily (50 mg/day; 1 week), then one pill daily (70 mg; 1 week) based on acceptable tolerability and clinical need). If 70 mg is not tolerated, downward titration to 50 mg/day can occur. For the remaining treatment

(weeks 4-12), the optimized LDX dose (50 or 70 mg/day) will be maintained. For the Stage 2 randomized maintenance (double-blind) treatment, a similar approach to dose-optimization will be followed. LDX down-titration for Stage 1 and Stage 2: 70 mg to 50 mg for 2 days, then 30 mg for 2 days, to discontinue medications. At the end of Stage 2, participants on placebo will take the same number of pills as the active group to maintain the blind.

**Non-responders NB:** NB titration is described on pages 9-10 of the protocol. Participants on placebo will take the same number of pills as the active group to maintain the blind. Participants will be cautioned against stopping the NB abruptly. For NB, taper off is not medically necessary for participants on the study medication for 4 weeks or less.

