**Assessments:** We will evaluate and monitor blood pressure and heart rate because studies have found that patients with obesity treated with NB have significantly lower drops than placebo in systolic BP changes (-0.4 vs. -2.1), diastolic BP (-0.1 vs -1.0), pulse rate (1.0 vs -0.1) (Greenway et al., 2010). Blood pressure and heart rate will be measured during all evaluation visits. Two readings will be taken at each assessment. In the event of systolic blood pressure  $\geq$ 160 mm Hg and/or diastolic blood pressure  $\geq$  100 mm Hg, or an increase in heart rate of  $\geq$ 15 bpm (from baseline), the study physician will be notified and will determine whether additional intervention and/or medication discontinuation is warranted. Liver function. Participants with severe hepatic disease will be excluded if this is detected at baseline, per exclusion criteria. Liver function will also be repeated in the Stage 2 RCT for non-responders who are randomized to NB or placebo at month-1 clinic visits. The study physician will review results of a hepatic panel prior to the start of treatment and throughout treatment. Any changes and out-of-range values will be flagged immediately by research clinicians, and the study physician will determine whether additional intervention and/or medication discontinuation is warranted.

Given the uncertain effects of medication during pregnancy, the following precautions will be taken for women of reproductive age who are sexually active: 1) a pregnancy test will be required at Stage 1 and Stage 2 (but only for those who will be re-randomized to treatment in Stage 2), 2) will be required to use a reliable method of birth control while she is in the study and to alert the research team if she departs from her birth control plans or if, in spite of adherence to these plans, she thinks she might be pregnant, and 3) if a woman becomes pregnant after study entry, her medication will be discontinued.

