**Plan for Determining Seriousness of Adverse Events:**

**Serious Adverse Events:** In addition to grading the adverse event, the PI will determine whether the adverse event meets the criteria for a Serious Adverse Event (SAE). An adverse event is considered serious if it results in any of the following outcomes:

1. Death;

2. A life-threatening experience in-patient hospitalization or prolongation of existing hospitalization;
3. A persistent or significant disability or incapacity;
4. A congenital anomaly or birth defect; OR
5. Any other adverse event that, based upon appropriate medical judgment, may jeopardize the subject's health and may require medical or surgical intervention to prevent one of the other outcomes listed in this definition.

An adverse event may be graded as severe but still not meet the criteria for a Serious Adverse Event. Similarly, an adverse event may be graded as moderate but still meet the criteria for an SAE. It is important for the PI to consider the grade of the event as well as its "seriousness" when determining whether reporting to the IRB is necessary.

Plan for events to the Yale IRB that are unexpected AND related AND involve risk of harm to subjects or others:

The PIs will report any incident, experience, or outcome that meets all three of these conditions to the IRB immediately:

1. Unexpected (in nature, specificity, severity, or frequency); given (a) the research procedures described in the protocol-related documents, such as the IRB-approved protocol and informed consent document and (b) the characteristics of the subject population being studied; AND
2. Related or possibly related to participation in the research (possibly related means there is a reasonable possibility that the incident, experience, or outcome may have been caused by the procedures involved in the research); AND
3. Suggests that the research places participants or others at greater risk of harm (physical, psychological, economic, legal, or social) than previously known or recognized.

Unanticipated Problems Involving Risks to Subjects or Others (UPIRSOs) may be medical or non-medical in nature, and include – but are not limited to – *serious, unexpected, and related adverse events* and *unanticipated adverse device effects*. Adverse events are reportable to the IRB as UPIRSOs only if they meet all 3 criteria listed above.

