These UPIRSOs/SAEs will be reported to the IRB in accordance with IRB Policy 710, using the appropriate forms found on the website. All related events involving risk but not meeting the prompt reporting requirements described in IRB Policy 710 should be reported to the IRB in summary form at the time of continuing review and/or a current DSMB report. If appropriate, such summary may be a simple brief statement that events have occurred at the expected frequency and level of severity as previously documented.

Plan for reporting adverse events to co-investigators on the study, as appropriate the protocol's research monitors, e.g., study sponsors, funding and regulatory agencies, and regulatory and decision-making bodies:  
For the current study, the following individuals, funding, and/or regulatory agencies will be notified:

- i. All Co-Investigators listed on the protocol
- ii. National Institutes of Health

The investigators will conduct a review of all adverse events upon completion of every study subject. The investigators will evaluate the frequency and severity of the adverse events and determine if modifications to the protocol or consent form are required.

Procedures for providing follow up care:

Medical monitoring will occur at all clinic and follow up visits and medical care will be provided if warranted. If a study participant experiences any psychiatric symptoms or distress (e.g., depressive symptoms or suicidality) at any stage of study participation he/she will receive short-term treatment and support from the study treatment team (including psychologists and a psychiatrist) and will be connected to a local emergency department (e.g., the Crisis Intervention Unit at Yale-New Haven Hospital) and his/her physician or therapist for ongoing care.

Measurement and reporting of subject accrual, adherence to inclusion/exclusion criteria.

Review of the rate of subject accrual and adherence to inclusion/exclusion criteria will occur regularly by the PI and co-Investigators and yearly by the safety officer. These reviews will help to assure that participants meet eligibility criteria and ethnic diversity goals outlined in the grant proposal.

Measurement and reporting of participant treatment completion rates.

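### Figure 2 schedules no adverse-event collection at the two follow-up visits, while the safety plan implies it continues; no AE/SAE end date or pregnancy-outcome follow-up is stated

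*Combined protocol and SAP*

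**What the plan says.** The Assessment Procedures paragraph (Section I, item 4) makes Figure 2 the schedule of measures.

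- **Figure 2.** The row "Adverse Events" is blank at baseline, marked at months 1 to 6, and blank in the last column, which covers both follow-up visits. The row "EDE-Q-I, BDI-II, GLTEQ, Weight, BP, HR" is marked in every column, follow-up included.
- **Perceptions of Treatment.** AE checklists are tied to clinic visits, with no stopping point.
- **Data and Safety Monitoring Plan, measurement and reporting of adverse events.** Collection is described as continuing. Serious or unanticipated events go to the NIH and the IRB within 48 hours. Neither statement is limited to the treatment months.
- **Data and Safety Monitoring Plan, procedures for follow-up care.** "Medical monitoring will occur at all clinic and follow up visits and medical care will be provided if warranted". Just above this, the investigators undertake to review all AEs when each participant completes.
- **SAE definition.** One criterion is "A congenital anomaly or birth defect".
- **Minimizing Risks, Assessments paragraph.** Women are to tell the team of a suspected pregnancy while in the study, and "if a woman becomes pregnant after study entry, her medication will be discontinued". No follow-up of the pregnancy is described.
- **Medication Titration & Taper.** "LDX down-titration for Stage 1 and Stage 2: 70 mg to 50 mg for 2 days, then 30 mg for 2 days". The NB treatment section describes a 7-day taper for those on medication longer than 4 weeks.

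**The concern.** The grid and the safety plan lead staff to do different things after month 6. Under the grid, nobody asks about AEs at the two follow-up visits. Under the safety plan, collection goes on.

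Three things are at stake:

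- **Events after the final stop.** LDX and NB are both tapered at the end of Stage 2, and participants are cautioned against stopping NB abruptly. Events in the taper or afterwards would reach the database only if someone volunteered them.
- **Comparability of counts.** Events would be solicited monthly to month 6 and only spontaneous afterwards. Any rate for the follow-up year would be a floor and could not be set beside the on-treatment rate. The cost-effectiveness section tracks outside treatment contacts through 18 months, so a hospitalisation could enter the cost data with no scheduled AE record.
- **Pregnancy.** The plan foresees pregnancy on study and lists a birth defect as an SAE, but schedules nothing that would establish the outcome.

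**Working it through.** **1. Length of participation.** Inclusion criterion 7: "Be available for participation in the study for up to 18 months (3 month + 3 month treatment plus 12 month follow up". 3 + 3 + 12 = 18 months, which agrees with the plan.

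**2. Reading the grid.** There are eight columns: baseline, months 1 to 6, and follow-up. The AE row has six marks, in months 1 to 6. The row with BDI-II, weight, BP and HR has eight marks, and the row for new treatments started is also marked at follow-up. The blank AE cell is therefore unlikely to be a fault of table extraction.

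**3. Time without a scheduled AE entry.** Follow-up visits fall at 6 + 6 = month 12 and 6 + 12 = month 18.
- Uncovered: 18 − 6 = 12 months; 12/18 = 67%.
- From the last AE entry to the next visit of any kind: 12 − 6 = 6 months.

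**4. Which drug stops are covered.**

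| Group | Last active study drug stops | Scheduled AE entries afterwards |
|---|---|---|
| LDX responders re-randomised to placebo | End of Stage 1 | Months 4, 5, 6 |
| LDX non-responders, as regards LDX | Before Stage 2 drug starts | Months 4, 5, 6 |
| Responders continuing LDX | End of Stage 2 | None |
| Non-responders given NB | End of Stage 2 | None |
| CBT only | No study drug | Not applicable |

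The LDX down-titration takes 2 + 2 = 4 days and the NB taper 7 days. The text does not say whether these come before or after the month-6 visit.

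**5. Approximate numbers.** Two Stage 1 arms of 60 receive LDX, so 120 people. The power section expects about 80 responders. Split equally, about 40 end Stage 2 on LDX. If the other 40 all enter the NB comparison and are also split equally (an assumption, as no ratio is stated), about 20 end on NB. That makes about 40 + 20 = 60 people, before dropout, who stop active drug at the final Stage 2 stop.

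**6. Timing of births.** Assumption: term is 38 weeks from conception, with 52.18/12 = 4.35 weeks per month. 38/4.35 = 8.7 months.
- Conception at month 0: birth at about 0 + 8.7 = month 8.7.
- Conception at month 6: birth at about 6 + 8.7 = month 14.7.

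All such births fall after the last AE entry and before the month-18 visit. For shorter gestations, delivery by month 6 needs conception before month 6 − 4.6 = 1.4 (20 weeks from conception) or before month 6 − 5.98 = 0.02 (26 weeks). At 30 weeks (6.9 months) it is not possible for an on-treatment conception. The pregnancy-test row is marked at baseline and month 3 only.

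**The case against.** The case for leaving the grid alone has several sound parts.

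- **Figure 2 is a visit schedule and does not define a reporting cut-off.** This stands. The 48-hour rule and the description of collection as continuing have no month-6 limit. A reader might infer that later hospitalisations or cardiovascular events cannot be recorded as AEs; the documents do not say so. What is missing is a scheduled question.
- **The quoted sentence promises medical monitoring and care, not AE logging.** This stands too. BP, HR, weight, BDI-II, lipids, HbA1c and glucose are taken at follow-up, so monitoring does happen. The firmer conflict is between the grid and the statement that collection continues, together with the review of all AEs at completion. Measurements do not attribute or grade events as the safety plan requires.
- **Most LDX stops at the end of Stage 1 are covered.** Correct, as step 4 shows. It would be wrong to say that post-discontinuation events in general are lost, or that every arm is under-counted after its last dose: CBT-only participants have no last dose.
- **The Background's question about stopping LDX concerns durability and relapse.** Correct. Those outcomes are measured at follow-up, so the point does not leave that question unanswered.
- **It is too strong to say that every birth defect is missed or that the criterion can never be met.** Agreed. Women must report a suspected pregnancy throughout the study, an anomaly may be known before birth, and a very early delivery by month 6 is possible.
- **Ending checklists of common drug effects when treatment ends is defensible.** As a choice it is, but the plan does not state that choice, and the safety plan points the other way. Consent pages are not in the text reviewed and may say more on pregnancy.

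**Conclusion.** The concern holds in a limited form. The grid schedules AE collection at months 1 to 6 and none at follow-up; the safety plan implies that collection goes on to completion; and no AE or SAE end date is given. If the grid is followed, events after the final Stage 2 stop have no scheduled capture for 6 months or more, and possibly none during the taper. The 67% figure describes calendar time, all of it off study treatment, and should not be read as a share of drug exposure. The outcome of a pregnancy begun on study medication has no scheduled capture in the text reviewed, although term births would fall within the participant's time on study. The birth dates rest on the assumed 38 weeks; the count of about 60 people rests on full entry to Stage 2 and equal splits. No efficacy analysis, sample size or error rate is affected. This is a change worth making to the safety data, and a cheap one.

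**What to change.** 1. In Figure 2, mark Adverse Events, at minimum SAEs and pregnancy outcome, at both follow-up visits. Ask about the whole interval since the previous visit, so that the month-12 enquiry also covers the taper.
2. State the end date for AE and SAE collection once, and make Figure 2, the adverse-event reporting paragraph and the follow-up care paragraph agree with it.
3. State that the outcome of any pregnancy begun on study medication will be recorded, so that the birth-defect criterion can be assessed.

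The cost is one row of the grid and a short enquiry at two visits that are already held and for which participants are already paid (Section VI, item 2), with occasional contact about a pregnancy. The drawback is more unrelated events to log over a year. No dose or treatment rule changes.

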### 3. Limits of Rules

There are other situations that could occur that might warrant stopping the trial and/or including a section on the safety report entitled “Other situations that have occurred since the last safety report that warrant discussion” to allow for communication of concerns.

Finally, as currently outlined above, the DSMB has the authority to stop the trial following any serious adverse event or following reviews of adverse events.

d. For multi-site studies for which the Yale PI serves as the lead investigator: NA

1. How will adverse events and unanticipated problems involving risks to subjects or others be reported, reviewed and managed? *Write here*
2. What provisions are in place for management of interim results? *Write here*
3. What will the multi-site process be for protocol modifications? *Write here*

13. **Statistical Considerations:** Describe the statistical analyses that support the study design.

### DATA ANALYSIS

Baseline demographic and clinical characteristics for randomized groups will be compared using chi-square tests for categorical variables, and ANOVA or Kruskal-Wallis tests for continuous variables. Continuous variables will be examined for adherence to normal distribution using normal probability plots and Kolmogorov-Smirnov tests. If normality not satisfied and transformations do not help with achieving normality, alternative analytic strategies will be considered such as generalized estimating equations or nonparametric methods. Dropouts and completers will be compared. Analyses will be intent-to-treat; patients will be followed regardless of treatment completion to minimize missing data. Primary outcomes will be tested at two-sided 0.05 significance level. Secondary analyses will be adjusted for multiple tests using Bonferroni correction.

Overall Data Analysis Strategy will involve MIXED EFFECTS MODELS (Diggle et al, 2002, Gueorguieva & Krystal, 2004) to compare treatments. These models allow for different numbers of observations per subject, use all available data on each subject, and are unaffected by randomly missing data. Further advantage is capacity to test and account for individual-difference contributions to treatment outcomes (Cudeck, 1996; Cudeck & Klebe, 2002; Hedeker et al., 1996; Hedeker & Gibbons, 1996; Singer, 1998). They provide flexibility in modeling the correlation structure of data. In models for each outcome, we will include fixed effects of time, treatment, and interaction between time and treatment, and random subject-level effects. Because we cannot a priori predict the shape of responses over time in each arm of the trial we will first treat time as a categorical predictor and will then test for polynomial trends over time. We will consider different error structures (e.g., AR1, independence) and select the best fitting one based on information criteria. We will

compare dropout patterns between groups and if there are concerns of informative dropout or informative intermittent missing data, we will use pattern mixture models (Hedeker & Gibbons, 1997) to perform sensitivity analyses.

(1) **STAGE 1 – Primary Outcomes Aim 1 and Secondary Outcomes Aim 2a:** Compare LDX and CBT effects, alone and in combination, for acute BED outcomes. Analyses examining the co-primary outcomes (reduction in binge-eating and percent weight loss) and examining the secondary outcomes (binge remission, eating disorder psychopathology, depression, metabolic variables) will be intent-to-treat using mixed-effects models per the overall strategy described above. Mixed-model analyses on continuous (or pseudo-continuous) data will use SAS PROC MIXED; mixed-model analyses on binary variables will use SAS PROC GLIMMIX. Logistic regression will be used for categorical outcomes (i.e., remission from binge-eating (defined as 0 binges/past 28 days on EDE interview). Significantly greater reductions in binge eating in CBT and CBT+LDX groups compared to LDX, and weight loss in LDX and CBT+LDX compared to CBT will be considered supportive of our primary aim hypotheses. We do not anticipate significant differences between CBT and CBT+LDX on binge eating and between LDX and CBT+LDX on weight loss but the mixed model approach will allow us to estimate the magnitude of the effects with associated confidence intervals.

(2) **STAGE 1 – Secondary Outcomes Aim 2b:** Explore conceptually and empirically supported predictors, moderators, and mediators for the primary outcomes (reductions in binge-eating and weight loss) and secondary categorical outcome (binge-eating remission). We will use the Kraemer et al (2002) approach to assess predictor, moderator and mediator effects by adding potential predictor, moderator and mediator variables to the models above. Predictors will be identified as variables with significant main effects on the outcome, moderators as variables with significant interactions with treatment on the outcome, and mediators will need to be significantly affected by treatment, to be related to the outcome and have main or interactive effects with treatment on the outcome. We will explore two empirically-supported predictors and moderators of BED outcomes – overvaluation of shape/weight (EDE) and depression (BDI-II) ([name], Masheb et al., 2012; [name] et al., 2013). It is necessary to test previous findings to establish them specifically for CBT and LDX treatments to inform prescription (i.e., for whom these “leading” treatments work best).

Finally, we expect that “rapid response” will have differential prognostic significance for CBT and LDX. Based on our prior methods ([name] et al., 2006; [name], White, et al., 2012; Masheb & [name], 2007), we hypothesize that overall rapid response will predict superior outcomes in both treatments (i.e., greater weight losses in LDX and greater reductions in binge-eating in both CBT and LDX) and that non-rapid-response will predict no further improvement in LDX but not for CBT (where gradual improvement is expected). In terms of mediators, per Kraemer et al (2002) models, we will explore whether differential symptom changes during treatment are associated with subsequent longer-term primary outcomes (binge-eating and weight loss). Repeated (and early) assessments of eating behaviors and cognitions (EDE-Q-I, TFEQ) constructs relevant to CBT, food-reward constructs (FCI-II, PFS) and executive control (Trails, BIS, DDT) constructs relevant to LDX, food-reward (FCI-II, PFS) constructs relevant to NB, and more general conceptually supported constructs (depression (BDI-II)), will yield relevant change variables for analyses of mediation (i.e., testing subsequent changes in binge-eating and weight). These analyses are exploratory and hence may be underpowered. However, they will provide valuable information in the form of variability estimates and effect size estimates for future more definitive studies.

(3) **STAGE 2 – Primary Aim 1:** Among Responders to Stage 1 treatments with LDX (i.e., LDX and CBT+LDX), compare LDX to placebo as a treatment maintenance strategy. The primary outcome will be “relapse” to DSM-5 level of once-weekly binge-eating and secondary outcomes will be binge-eating frequency, weight loss, eating-disorder pathology, and depression. For the primary outcome (predicting relapse), we will follow

analytic strategy of studies testing medication for maintenance (i.e., fluoxetine) for bulimia nervosa (Romano et al (2002) and for anorexia nervosa (Walsh et al (2006) which was recently used in the Shire maintenance study of LDX for BED (Hudson et al., 2015). Stage 2 LDX and placebo will be compared on the proportion of Stage 1 responders who “relapse” using chi-squared tests and Cox Proportion Hazards Tests; we will explore further using survival analyses to estimate whether time to relapse differs between LDX and placebo. For the secondary outcomes, we will use mixed effects models to assess whether there is significant change in binge eating or weight loss between the group who continue LDX treatment and the group who receive placebo. We anticipate that subjects randomized to LDX maintenance will maintain better outcomes than patients randomized to placebo. We will also perform parallel analyses on all three groups (CBT, LDX, CBT+LDX) to compare outcomes at the 6-month time point (i.e., comparing 3-month CBT and 6-month two-stage treatments).

(4a) **STAGE 2 – Secondary Aim 1:** Explore LDX and CBT effects, alone and in combination, for longer-term BED outcomes. Our two-stage design will also allow us to also compare CBT (i.e., Stage 1 CBT-only short-term) versus the Stage 2 LDX/placebo maintenance treatment (i.e., Stage 2 LDX/placebo following Stage 1 LDX or Stage 1 CBT+LDX) for longer-term outcomes through 18 months. This will inform clinical questions regarding whether LDX maintenance treatment following either acute LDX treatment or acute combined CBT+LDX differ and whether it offers any additional benefits over acute CBT-only (4b).

**STAGE 2 – Secondary Aim 2:** Among Non-responders to Stage 1 treatments with LDX, Explore the effectiveness of switching to an alternative medication (NB versus placebo). Primary outcomes will be reducing binge-eating and reducing weight and secondary outcomes will be binge-eating remission, eating-disorder pathology, and depression. We will use similar analyses to Primary Aim 1: mixed models for the continuous outcome variables and logistic regression for categorical (remission) variable.

**(5) Secondary Aim:** Generate estimates of cost-effectiveness. We will compute within-study costs for CBT, LDX, CBT+LDX and SMART Stage 2 interventions. Repeated assessments will track additional clinician visits and medication use in our RCT as well as outside treatment contacts through the 18-months. SF-12, administered pre- and post-treatments and at follow-ups, will be used to calculate quality-adjusted life years (QALY) following established methods (Revicki et al., 2005) also used in BED studies of cost-effectiveness specifically of LDX (Agh et al., 2016) and CBTgsh (Lynch et al., 2010; Dickerson et al., 2011), as well as for obesity (Tsai et al., 2005; Malone et al., 2005) including obesity medications (Ara et al., 2012), and for similar SMART designs (switching medication for initial non-responders) in depression (Singh et al 2017). We will calculate incremental cost-effectiveness ratios (ICERs) for the various arms; in these ICERs, the numerator will be the incremental medical cost and the denominator will be the incremental effectiveness of the specific treatment compared to CBT. Confidence intervals for the ICERs will be determined using non-parametric bootstrapping. These ICERs will be compared to the two previous BED (Agh et al., 2016; Lynch et al., 2010) analyses and inform subsequent more definitive larger-scale effectiveness studies.

**POWER ANALYSIS:** We calculated our sample size to have at least 80% power at 2-tailed alpha level 0.025 (adjust for 2 outcomes) to detect clinically meaningful effects in Stage 1 for co-primary outcomes (binge eating and weight loss) and Stage 2 for primary outcome (relapse by initial Responders) at 2-tailed level of 0.05 according based on documented effects of the two treatment components (LDX and CBT). In Stage 1, with 180 subjects total (60 per treatment group), accounting for up to 20% dropout, we can detect medium effect sizes ( $d=0.64$ ,  $f=0.32$ ) for the between group comparisons with more than 80% power at two-sided alpha level of 0.025. These effect sizes are smaller than the effect sizes calculated based on data (Telch et al., 1990; [name] et al., 2005; McElroy et al., 2015, McElroy 2016) which ranged  $d=0.69$  to  $d=0.78$  for the comparison of CBT to LDX on binge-eating and was  $d=1.53$  for LDX vs CBT on percent weight loss. Dropout

rate estimated based on completion rates for [name] RCTs with BED: 87% in [name] & Masheb, 2005; 84% in [name], White et al., 2014; and previous grant 2R01 DK49587-15 testing stepped care multi-modal treatment and obesity medication along with the LDX RCTs (McElroy et al., 2015, 2016). For binary outcomes (remission), we can detect the following clinically meaningful differences in proportions (63% vs 35%, 66% vs 38%) at 2-tailed alpha of 0.025 in Stage 1. These are in line with observed proportions for CBT (62% by Wilson et al (2010); 64% by Striegel-Moore et al. (2010); LDX (40% and 36% by McElroy et al (2015; 2016) in BED subjects uncomplicated by co-morbidity. Thus, we are well powered for realistic and meaningful effect sizes for both primary and secondary outcome variables. In Stage 2, we expect to randomize 65-70% of subjects as Responders (per McElroy et al 2017); thus we anticipate to have about 80 subjects from the LDX and CBT+LDX groups for the comparisons of interest. Assuming further 20% dropout, we will have 64 subjects with complete data at the end of Stage 2. With this sample size, we have 89% power at two-sided alpha level of 0.05 to detect differences in relapse reported by Hudson et al (2015) of 4% vs 32% (LDX vs placebo). We would have over 80% power to detect differences for the following rates between placebo and LDX: 10% vs 39%, 15% vs 46%, 25% vs 58%.

